2.10.3.2.2. Short Form-36

The SF-36 individual subscales (Physical Functioning (PF), Role-Physical (RP), Bodily Pain (BP), General Health (GH), Vitality (VT), Social Functioning (SF), Role-Emotional (RE) and Mental Health (MH)) , component measures (Physical Health Component Score and Mental Health Component Score) and total score (Physical Health Component Score + Mental Health Component Score) will be analyzed using an Analysis of Covariance model with baseline value as a covariate and treatment and region (country) as factors. Observed values, and change from baseline will be summarized using mean, standard deviation, median, minimum and maximum.

Derivation of the SF-36 subscales are defined in section 2.15.

2.11. Primary and Final Analyses

There are two planned analyses for the study: the primary analysis and the final analysis. The primary analysis is not an interim analysis. All subjects will have finished their treatment and the 12-week primary endpoints will be locked. Thus, the primary analysis is not subject to an alpha-spending penalty. No multiplicity adjustment is needed.

The primary analysis will be performed in a partially unblinded fashion. The generated tables will be presented using the actual treatment groups, but information pertaining to the unblinded treatment received by individual subjects will be blinded. So thus, the results will be known, but the individual subjects will still be blinded.

The primary analysis will be performed once all subjects have completed 3 months of treatment. The following variables will be included in the primary analysis:

Primary Objective

Percent Change in Total Body Less Head (TBLH) Lean Body Mass obtained from the DXA scan at 3 Months.

Secondary Objectives

Hip Bone Mineral Density (BMD) obtained from the DXA scan at 3 Months.

Total Lean Body Mass (TLBM) obtained from the DXA scan at 3 Months.

Appendicular Lean Body Mass (ALBM) obtained from the DXA scan at 3 Months.

Exploratory Objectives

6 Minute Walk Test

Short Physical Performance Battery (SPPB)

Short Form-36 (SF-36) Quality of Life Questionnaire

All analyses as indicated in the SAP will be presented for the final analysis.

2.12. Other Analyses

There are no other analyses planned for this study.

2.13. Analysis of Subgroups

There are no subgroup analyses planned for this study, but there is a plan to perform analyses to test for significant factor effects.

At the 3 month and 6 month analyses, we will test for a significant sex effect. Sex will be added as a factor into the ANCOVA models with least squares means and 95% confidence intervals being presented by treatment and sex. P-Values will be presented for the sex effect, treatment effect and sex*treatment interaction.

2.14. Sample Size and Power Considerations

Power Considerations Prior to Study Start

Based on the observed change in total lean body mass information from previous studies (as percentage change in total lean body mass information is not available), it seems reasonable to estimate the placebo-adjusted difference in total lean body mass for the 0.5 mg group to be 0.5 kg and 1.0 kg for the 1 mg group. For the purpose of power calculations, the 2 mg group is extrapolated to show a 1.5 kg adjusted difference. The estimate of standard deviation, based on information from the previous study, is estimated to be 1.3. A sample size of 30 subjects per treatment group yields 84% power to detect a difference between the 1 mg treatment group and placebo and 99% power to detect a difference between the 2 mg treatment group and placebo.

Even though the sample size estimate is based on the observed change in total lean body mass, we believe that the resulting calculations are reasonable for the analysis of percentage change in body less head lean body mass.

120 subjects are required to have baseline and 3 months' post-treatment data to observe the power indicated above. The protocol was written to enroll 120 subjects, assuming that there would be no dropouts.

Power Considerations Once Approximately Half of the Subjects Completed Month 3

Once approximately half of the subjects had 3 month DXA data, the data was reviewed in a blinded fashion.

Modifications to the pre-study assumptions was considered appropriate.

A placebo adjusted change of 1.6, 2.4 and 4.1 for the 0.5 mg, 1.0 mg and 2.0 mg active groups respectively with a standard deviation estimate of 2.0 seemed to be more reasonable.

Under these assumptions, the power calculations are as follows:

- Placebo vs. 0.5 mg VK5211 – 26 subjects per treatment group yields 80% power
- Placebo vs. 1.0 mg VK5211 – 16 subjects per treatment group yields 90% power
- Placebo vs. 2.0 mg VK5211 – 7 subjects per treatment group yields 90% power

Based on these numbers, it seems reasonable to randomize 104 subjects to complete approximately 92 (approximately 23 subjects per treatment group to complete). Thus, the decision was made to stop enrollment prior to randomizing all 120 subjects.

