2.10.2. Secondary Efficacy Assessments

2.10.2.1. DXA Scans

The total lean body mass, hip bone mineral density, total body mass and fat mass, appendicular lean body mass and bone turnover markers will be analyzed using an Analysis of Covariance model with baseline value as a covariate and treatment and region (country) as factors.

Observed values, percentage change, percent change from baseline and absolute change from baseline will be summarized using mean, standard deviation, coefficient of variation (CV%), median, minimum and maximum. A 95% confidence interval on the placebo adjusted change from baseline will also be presented.

The analysis of the values obtained from the central reader will be the primary analysis. The values obtained from the site (as recorded on the CRF) after applying a correction factor to adjust for the different DXA machine types will also be analyzed.

The definition of valid DXA from the central reader is as follows:

A valid DXA indicates the scan was acquired under the correct scanner setting, includes the entire region of interest and is free of artifacts that would affect quality results such as jewelry, surgical hardware, etc. Bioclinica technologists specifically trained on DXA scan analysis review the scans submitted to Bioclinica visually for those criteria as well as technical parameters such as scan mode, voltage setting, etc.

The initial concept behind the Month 3 analysis is that the subject would be on drug for at least 56 days and that the DXA measurement would be taken shortly (within 14 days) after the subject completed therapy. Thus, subjects who did not have at least 56 days of treatment or did not have their “Month 3” DXA within the allotted time was planned to be excluded from the analysis. It is important to note that the “Month 6” analysis is performed after the subject has been off therapy, so some of the data excluded from the Month 3 analysis will be included in the Month 6 analysis.

Given the variation of actual dosing and the timing of the actual DXA scan, there will be two definitions of a valid DXA for analysis purposes: “The Stringent Definition of Valid DXA” and “The Liberal Definition of Valid DXA”.

The stringent definition of valid DXA is as follows:

The subject must be on treatment for at least 56 days, have a valid baseline DXA and a DXA within 14 days after stopping treatment. (This is the definition as indicated in the protocol.)

The liberal definition of valid DXA is as follows:

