2.16. Handling Missing Data

Listings will be provided for all data. Descriptive statistics will be provided for all planned visits as provided on the Case Report Forms (CRFs).

Study days will be analyzed using the study days as reported in the Case Report Form. Likewise, unscheduled visits will not be reassigned a visit number based on the visit date.

Dates related to the adverse events and medications will be imputed using the rules below in an effort to categorize them properly into the summary tables.

Imputing partial or missing start dates:

- If the year is unknown, then the start date will not be imputed. The date will remain missing.
- If the month is unknown and the year is the same as the first dose date of the study, then impute the month and day of the date to be equal to the first dose month and day. Otherwise, impute the month as January.
- If the day is unknown and the month and year are the same as the first dose date of the study, then impute the day to be equal to the day of the first dose. Otherwise, impute the day as '01'.

Impute partial or missing stop dates:

- If the year is unknown, then the stop date will not be imputed. The date will remain missing.
- If the month is unknown, impute the month as December.
- If the day is unknown, impute the day to be the last day of the month.

If an imputed stop date is greater than the date of study completion/discontinuation date of the study, then the imputed stop date will be set equal to the date of completion/discontinuation date.

The imputed dates will be stored in the analysis datasets along with the original dates as recorded by the sites.

Efficacy and safety data collected at early termination visits will be included in the Month 3 and Month 6 analyses. Data collected on or prior to Day 112 (Day 84 + 28 Days) will be used for the Month 3 (Day 84) analyses. Data collected after Day 112 will be assigned to the Month 6 (Day 168) analyses.

For efficacy endpoints that have multiple post-baseline visits, last observation carried forward will be presented for the Month 3 and Month 6 visits. The DXA (both central reader and CRF), Six Minute Walk, Short Physical Performance Battery and SF-36 Scales will also have a multiple imputation method performed to address missing data as discussed in section 2.17.

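### The SAP's revised plan quotes 80% power for 0.5 mg at 26 per group but expects about 23 completers per group, where its own inputs give about 76%

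*SAP*

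**What the plan says.** SAP 2.14 contains two power statements.

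- **Pre-study.** With 30 per group and SD 1.3, it states 84% power for 1 mg and 99% for 2 mg. It assumes a 0.5 kg difference for 0.5 mg but gives no power for that dose. It counts the 120 as subjects with baseline and Month 3 data, needed as "post-treatment data to observe the power indicated above", and notes that the protocol allowed for no dropouts.
- **Mid-study.** When about half the subjects had Month 3 DXA data, "the data was reviewed in a blinded fashion". Differences of 1.6, 2.4 and 4.1 for the three doses, "with a standard deviation estimate of 2.0 seemed to be more reasonable". For 0.5 mg against placebo, "26 subjects per treatment group yields 80% power". For 1.0 mg the figures are 16 per group and 90%, and for 2.0 mg they are 7 per group and 90%. The section then concludes: "Based on these numbers, it seems reasonable to randomize 104 subjects to complete approximately 92 (approximately 23 subjects per treatment group to complete". Enrollment was stopped short of 120 on that basis.

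The section gives neither the power at 23 per group nor the alpha.

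**The concern.** The group size that earns 80% for 0.5 mg equals the number randomized per group, while the same sentence expects about three fewer per group to complete. The section's pre-study convention is to count subjects with data, and on that convention the revised plan does not expect to have the 26 that its 80% needs. Of the three figures offered as the basis for 104, this is the only one that requires more than 23 per group.

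What is at stake is how a 0.5 mg result will be read. Protocol 5.3 expects the chosen doses to allow the minimal effective dose to be estimated, though it sets no power requirement. Someone weighing a null result at 0.5 mg could take 80% as the power of the 104-subject plan, which overstates it on the SAP's own inputs.

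**Working it through.** **Inputs from SAP 2.14.** Differences 1.6, 2.4 and 4.1; SD 2.0; stated sizes 26, 16 and 7 per group; 104 randomized and about 92 completing. With 1:1:1:1 allocation, 104/4 = 26 and 92/4 = 23 per group. Implied loss is 1 − 92/104 = 11.5%.

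**Assumptions.** Two-sided alpha 0.05, consistent with the 95% confidence intervals in SAP 2.10.1. The 2.0 is used as the within-arm SD.

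**Method.** Two-sample t-test with n per group: noncentrality = difference / (SD × √(2/n)), df = 2n − 2, power from the noncentral t distribution.

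**Step 1: reproduce the stated sizes.**

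| Comparison | One fewer per group | Stated n | Power at stated n |
|---|---|---|---|
| 0.5 mg (1.6), target 80% | n = 25: 79.1% | 26 | 80.7% |
| 1.0 mg (2.4), target 90% | n = 15: 88.7% | 16 | 90.7% |
| 2.0 mg (4.1), target 90% | n = 6: 89.1% | 7 | 94.0% |

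The smallest sizes that meet the targets are exactly 26, 16 and 7. A normal approximation would give 25, 15 and 6, and four-arm error df would give 26, 16 and 6. The match supports the assumed alpha and shows that 2.0 was entered as the within-arm SD. It also shows that 26 has no spare subject.

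**Step 2: the same calculation at 23 per group.**

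- 0.5 mg: noncentrality = 1.6 / (2.0 × √(2/23)) = 2.71, df 44, power **75.6%**. With the four-arm error df (4 × 23 − 4 = 88) it is 76.5%.
- 1.0 mg: noncentrality = 2.4 / (2.0 × √(2/23)) = 4.07, power 97.8%.
- 2.0 mg: noncentrality = 4.1 / (2.0 × √(2/23)) = 6.95, power over 99.9%.

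For 0.5 mg the gap is 80 − 75.6 = 4.4 points (3.5 with four-arm df), so about 4.

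**Step 3: sensitivity for 0.5 mg.**

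| Analysed per group | 20 | 22 | 23 | 24 | 25 | 26 |
|---|---|---|---|---|---|---|
| Power | 69.3% | 73.6% | 75.6% | 77.4% | 79.1% | 80.7% |

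If adjusting for baseline reduces the SD to 2.0 × √(1 − r²), then 23 per group reaches 80% at r of about 0.32 (df 44) or 0.29 (df 87). The documents give no value for r.

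**Step 4: the pre-study benchmark.** Difference 0.5, SD 1.3 and 30 per group give 31.1% for 0.5 mg. The pre-study plan therefore held no high power at this dose.

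**The case against.** The SAP's sums are right, and it never claims 80% at 23. Both numbers stand close together in the section, so the loss is visible and only one derived figure is missing. That stands, and it is why this is not an arithmetic error.

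The gap is small beside the looseness of the inputs: at 23 per group, 80% would be reached with a difference of 1.69 instead of 1.6, or an SD of 1.89 instead of 2.0. No stated power target for 0.5 mg existed before the study, and the other two comparisons are comfortable. These points stand too, and they limit the weight.

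Twenty-three completers need not be the number analysed. On early withdrawals, SAP 2.16 says "Efficacy and safety data collected at early termination visits will be included in the Month 3 and Month 6 analyses", with Day 112 as the cut-off for Month 3. It also says that the DXA, among other endpoints, "will also have a multiple imputation method performed to address missing data". Protocol 4.3 replaces subjects who discontinue before Day 28. All of these could raise the number. The stringent valid-DXA rule in SAP 2.10.2.1 works the other way: "The subject must be on treatment for at least 56 days, have a valid baseline DXA", plus a scan within 14 days after stopping. The direction is therefore open. The planned ANCOVA could recover power, but the SAP's calculation credits none of this, so these routes do not make 80% the power of the plan as written.

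The 2.0 might be a pooled SD that contains the treatment effects. The variance of (0, 1.6, 2.4, 4.1) is 2.18, so the within-arm SD would be √(4 − 2.18) = 1.35 and power at 23 about 98%. On that reading, however, the required sizes would be 13, 8 and 4, not the 26, 16 and 7 that the SAP prints. The 76% follows the SAP's inputs as the SAP used them.

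**Conclusion.** The point holds as a reporting gap of minor severity. At the completer number the SAP itself plans, its own inputs give about 76% power for 0.5 mg, against the 80% quoted at 26 per group: about 4 points lower, at the lowest dose only. This rests on a two-sided 0.05 test, 2.0 as the within-arm SD, and 23 analysed per group without credit for baseline adjustment.

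A reader might infer three stronger things that the documents do not support.

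- **That the SAP miscalculated.** It did not; all three sizes reproduce.
- **That enrollment should have run to 120.** Keeping 26 completers at the implied loss would need 26 / (92/104) = 29.4, so 30 per group or 120 in all. But the documents set no requirement of 80% for 0.5 mg, and the other two doses keep about 98% and over 99.9% at 23.
- **That arm-specific effects show the review was not blinded.** The SAP describes it as blinded and does not say where the effects came from. Nothing here depends on that.

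**What to change.** In SAP 2.14, keep the record of the 26, 16 and 7 calculation and of the decision to stop at 104. Add a sentence stating that, at the planned 23 completers per group, power is about 76% for 0.5 mg, 98% for 1.0 mg and over 99% for 2.0 mg, with the alpha used. That keeps 80% from being carried forward as the 0.5 mg power of the 104-subject plan.

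The cost is a sentence or two, and a 0.5 mg figure about 4 points less favourable. Enrollment, alpha and the analysis method stay as they are.

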2.15. Randomization Scheme and Codes

The randomization details are documented in a separate randomization plan.

2.16. Handling Missing Data

Listings will be provided for all data. Descriptive statistics will be provided for all planned visits as provided on the Case Report Forms (CRFs).

Study days will be analyzed using the study days as reported in the Case Report Form. Likewise, unscheduled visits will not be reassigned a visit number based on the visit date.

Dates related to the adverse events and medications will be imputed using the rules below in an effort to categorize them properly into the summary tables.

Imputing partial or missing start dates:

- If the year is unknown, then the start date will not be imputed. The date will remain missing.
- If the month is unknown and the year is the same as the first dose date of the study, then impute the month and day of the date to be equal to the first dose month and day. Otherwise, impute the month as January.
- If the day is unknown and the month and year are the same as the first dose date of the study, then impute the day to be equal to the day of the first dose. Otherwise, impute the day as '01'.

Impute partial or missing stop dates:

- If the year is unknown, then the stop date will not be imputed. The date will remain missing.
- If the month is unknown, impute the month as December.
- If the day is unknown, impute the day to be the last day of the month.

If an imputed stop date is greater than the date of study completion/discontinuation date of the study, then the imputed stop date will be set equal to the date of completion/discontinuation date.

The imputed dates will be stored in the analysis datasets along with the original dates as recorded by the sites.

Efficacy and safety data collected at early termination visits will be included in the Month 3 and Month 6 analyses. Data collected on or prior to Day 112 (Day 84 + 28 Days) will be used for the Month 3 (Day 84) analyses. Data collected after Day 112 will be assigned to the Month 6 (Day 168) analyses.

For efficacy endpoints that have multiple post-baseline visits, last observation carried forward will be presented for the Month 3 and Month 6 visits. The DXA (both central reader and CRF), Six Minute Walk, Short Physical Performance Battery and SF-36 Scales will also have a multiple imputation method performed to address missing data as discussed in section 2.17.

2.17. Multiple Imputation Method

The reason for using the Multiple Imputation Method is to minimize bias, maximize use of available information and obtain appropriate estimates of uncertainty.

A variable is said to be missing at random (MAR) if other variables (but not the variable itself) in the dataset can be used to predict missingness on a given variable, and the missing variable is not dependent upon the study conduct or the investigational product. For example, if the subject did not attend a visit (or missed the test within a visit) due to reasons other than a treatment related adverse event, lack of therapeutic effect, discontinuation of study by sponsor,

A variable is said to be missing not at random (MNAR) if the value of the observed variable itself predicts missingness or the missing of the variable is related to study conduct or the investigational product. For example, if the subject did not attend a visit (or missed the test within a visit) due to a treatment related adverse event, lack of therapeutic effect, discontinuation of study by sponsor,

If a value is determined to be MAR, the value is eligible to be imputed using the multiple imputation method. If a value is determined to be MNAR, the value is not eligible to be imputed using the multiple imputation method and can be replaced with the worst-case scenario or excluded from the analysis.

There are 3 steps to the Multiple Imputation Method: 1) Imputation, 2) Analysis and 3) Pooling.

Imputation

Similar to single imputation (for example, last observation carried forward), missing values are imputed. However, the imputed values are drawn m times from a distribution rather than just once. At the end of this step, there should be m completed datasets to analyze. The distribution of the missing variable is determined by using other information contained in the study data by establishing correlations and determining other possible relationships. SAS's procedure PROC MI is used during the imputation step.

Analysis

Each of the m datasets is analyzed as defined in the SAP. At the end of this step there should be the results from m analyses.

Pooling

The m results are consolidated into one result by calculating the mean, variance, and confidence interval of the variable of concern. SAS's procedure PROC MIANALYZE is used during the pooling step.

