4.1. Post-text Table of Contents

The following post-text tables will be generated.

Table Number	Table Title
14.1.1.1	Summary of Screening Status – All Subjects
14.1.1.2	Summary of Subject Disposition – Safety Population
14.1.1.3	Summary of Subject Disposition – Intent-to-Treat Population
14.1.1.4	Summary of Subject Disposition – Per Protocol Population
14.1.2.1	Summary of Demographics and Baseline Characteristics – All Subjects
14.1.2.2	Summary of Demographics and Baseline Characteristics – Safety Population
14.1.2.3	Summary of Demographics and Baseline Characteristics – Intent-to-Treat Population
14.1.2.4	Summary of Demographics and Baseline Characteristics – Per Protocol Population
14.1.3.1	Summary of Medical History – Safety Population
14.1.4.1	Summary of Prior Medications – Safety Population
14.1.4.2.1	Summary of Concomitant Medications at Baseline Visit – Safety Population
14.1.4.2.2	Summary of Concomitant Medications Taken During the Treatment Period – Safety Population
14.1.5.1	Summary of Study Drug Administration – Safety Population
14.1.5.2	Summary of Study Drug Administration – Intent-to-Treat Population
14.1.5.3	Summary of Study Drug Administration – Per Protocol Population
14.2.01.1.1	Summary of Whole Body Dual Energy X-Ray Absorptiometry (DXA) scan – Total Body Less Head – Central Reader – Stringent Definition of Valid DXA - Intent-to-Treat Population
14.2.01.1.2	Summary of Whole Body Dual Energy X-Ray Absorptiometry (DXA) scan – Total Body Less Head – Central Reader – Multiple Imputation Method - Stringent Definition of Valid DXA - Intent-to-Treat Population
14.2.01.1.3	Summary of Whole Body Dual Energy X-Ray Absorptiometry (DXA) scan – Total Body Less Head – Central Reader – Sex Effect - Stringent Definition of Valid DXA - Intent-to-Treat Population
14.2.01.1.4	Summary of Whole Body Dual Energy X-Ray Absorptiometry (DXA) scan – Total Body Less Head – Central Reader – Liberal Definition of Valid DXA - Intent-to-Treat Population

Table Number	Table Title
14.2.01.1.5	Summary of Whole Body Dual Energy X-Ray Absorptiometry (DXA) scan – Total Body Less Head – Central Reader – Multiple Imputation Method - Liberal Definition of Valid DXA - Intent-to-Treat Population
14.2.01.1.6	Summary of Whole Body Dual Energy X-Ray Absorptiometry (DXA) scan – Total Body Less Head – Central Reader – Sex Effect - Liberal Definition of Valid DXA - Intent-to-Treat Population

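### SAP 2.17 sends drug-related missing values to an undefined worst case or to exclusion, so the imputation tables cannot test informative dropout; SAP 2.16 adds LOCF at Month 3 and at the off-drug Month 6 visit

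*SAP*

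**What the plan says.** **MI rule.** SAP 2.16 states that DXA (central and site readings), 6MWT, SPPB and SF-36 "will also have a multiple imputation method performed to address missing data". SAP 2.17 limits this to values judged missing at random (MAR). A value is missing not at random (MNAR) if, among other things, "the missing of the variable is related to study conduct or the investigational product"; the examples include treatment-related adverse events, lack of effect and the sponsor ending the study. Such a value is not imputed and "can be replaced with the worst-case scenario or excluded from the analysis".

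**Where MI is used.** SAP 4.1 lists MI tables for total body less head (TBLH) lean mass, the primary variable. In the ITT population with central reading these are 14.2.01.1.2, whose title ends "Multiple Imputation Method - Stringent Definition of Valid DXA - Intent-to-Treat Population", and 14.2.01.1.5, its liberal-definition counterpart. The stringent definition (SAP 2.10.2.1) requires at least 56 days on treatment, and the subject must "have a valid baseline DXA and a DXA within 14 days after stopping treatment".

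**LOCF.** SAP 2.16: "For efficacy endpoints that have multiple post-baseline visits, last observation carried forward will be presented for the Month 3 and Month 6 visits". SAP 2.10.2.1 notes that the Month 6 "analysis is performed after the subject has been off therapy".

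**Primary model.** SAP 2.10.1 specifies an ANCOVA at Visit 4 and names no missing-data method.

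**Protocol 9.6** rules out substitution of missing data in any calculation.

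**The concern.** Declining to impute suspected MNAR values under a MAR model is defensible. The difficulty is what replaces it. Two statisticians following SAP 2.17 could build different tables: one drops the subject, the other inserts a worst value of their own devising. Exclusion leaves out the very dropouts that a missing-data check is meant to examine. A single inserted value is not reliably conservative, because its direction depends on which arm lost the subject.

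This matters because the observed-data ANCOVA omits the same subjects, so its result needs a check that can speak to informative dropout. LOCF does not supply one for DXA at Month 3. Under Protocol 6.10, scans are scheduled only at Randomization, Visits 4 and 5, or early withdrawal, so there is no earlier scheduled post-baseline scan to carry forward.

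LOCF does act at Month 3 on 6MWT and SPPB, which are measured at Visits 2 and 3 and belong to the primary analysis package in SAP 2.11. At Month 6 it fills an off-drug value with an earlier one and so assumes persistence, although SAP 1.2 gives duration of drug effect as a purpose of follow-up.

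**Working it through.** **Inputs (SAP 2.14).** Effects 1.6, 2.4 and 4.1 at 0.5, 1.0 and 2.0 mg; SD 2.0 (no unit is given); 104 randomised to complete about 92.

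**The plan's own figures.** With a two-sided t-test at 5% (assumed; SAP 2.14 states no alpha), the smallest group sizes for 80%, 90% and 90% power are 26, 16 and 7, as the SAP states. Achieved power is 80.8%, 90.7% and 94.0%.

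**Number missing.** (104 − 92)/104 = 12/104 = 11.5%, and 12/104 = 3/26. With 104/4 = 26 per arm, 3 is the average number of non-completers per arm. How many would be MNAR, and in which arm, is not given, so k below is an assumption.

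**Option 1, exclusion.** Suppose k of 26 active subjects are lost and their true mean equals placebo, while the rest have effect d. The mean effect over all 26 is (1 − k/26)d, but the analysis estimates d. The overstatement is (k/26)d:

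| k | 0.5 mg | 1.0 mg | 2.0 mg |
|---|---|---|---|
| 1 | 0.06 | 0.09 | 0.16 |
| 3 | 0.18 | 0.28 | 0.47 |
| 6 | 0.37 | 0.55 | 0.95 |

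The observed-data ANCOVA carries the same bias, so exclusion adds no information.

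**Option 2, one fixed worst value.** The SAP gives no definition, so two were assumed: the lowest observed value in the subject's own arm, and the lowest in both arms. Simulation: 200,000 runs per cell, 26 per arm, unadjusted t-test, k = 3 missing in one arm only.

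*Losses on active* (mean difference; power):

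| Dose | Excluded | Own-arm lowest | Overall lowest |
|---|---|---|---|
| 0.5 mg | 1.60; 78% | 1.16; 48% | 0.95; 25% |
| 1.0 mg | 2.40; 98% | 1.95; 89% | 1.66; 73% |
| 2.0 mg | 4.10; 100% | 3.66; 100% | 3.17; 99.9% |

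The exclusion column treats the losses as random, so its power figures say nothing about the bias under option 1. With k = 1 at 0.5 mg, the differences are 1.45 (own-arm lowest) and 1.38 (overall lowest).

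*Losses on placebo, no true effect* (own-arm lowest to overall lowest):

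| k | Shift favouring drug | Two-sided rejection |
|---|---|---|
| 1 | 0.15 to 0.17 | about 5% |
| 2 | 0.30 to 0.35 | about 7% |
| 3 | 0.44 to 0.52 | about 10% |

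At k = 3 almost all rejections favour the drug. Arithmetic check: 0.444 × 26/3 = 3.85, or about 1.9 SD below the mean, which is plausible for the lowest of 23 values.

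**Month 6 LOCF.** Overstatement = (k/26) × (carried effect − true Month 6 effect). With k = 3 and the full Month 3 effect carried:

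| Effect retained off drug | 0.5 mg | 1.0 mg | 2.0 mg |
|---|---|---|---|
| None | 0.18 | 0.28 | 0.47 |
| Half | 0.09 | 0.14 | 0.24 |
| All | 0 | 0 | 0 |

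Under full washout, rejection is 5.8%, 6.7% and 9.4% with k = 3, and about 5% at every dose with k = 1. The number with an earlier scan but no Month 6 scan is not given.

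**Protocol 9.6.** LOCF, MI and worst-case replacement all substitute for missing data and so conflict with it. Exclusion and the observed-data ANCOVA do not.

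**The case against.** *The primary analysis is untouched.* It is true that neither rule feeds the Month 3 DXA ANCOVA. A reader might infer either that these rules distort the primary estimate or that the primary result is therefore safe. The documents support neither: SAP 2.10.1 names no imputation, and the same model silently omits the same subjects. The SAP also does not rank the MI tables. That they are supplementary is an inference from the word also in SAP 2.16.

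*The large figures rest on assumed definitions and one-arm losses.* This stands. Neither worst-case rule is in the SAP, and the simulation uses a t-test without baseline or country. A lower active-arm estimate is partly what a worst-case check is for. The power figures describe a sensitivity table, not the trial.

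*Few values will be missing.* Protocol 7.7 asks for Visit 4 procedures at early withdrawal. SAP 2.16 adds, for early-termination data: "Data collected on or prior to Day 112 (Day 84 + 28 Days) will be used for the Month 3 (Day 84) analyses". Protocol 4.3 replaces subjects who leave before Day 28, and ITT membership needs a post-baseline assessment. These lower the count. Uneven losses between arms could raise it, as could counting scans that fail the stringent definition as missing, which SAP 2.17 does not settle. Three of 26 should not be read as an upper limit.

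*Other checks exist.* The liberal-definition tables keep some subjects treated for under 56 days, but only those with a scan.

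*Month 6 is secondary.* This also stands. The efficacy objectives are at 12 weeks, observed values are summarised, and SAP 4.1 titles no LOCF table (the shells are in a separate file).

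**Conclusion.** The point holds for the MI rule. The choice is open, the worst case is undefined, and both options are weak: exclusion reproduces the observed-data bias of (k/26)d, and a fixed worst value can move the estimate either way. With an assumed 3 of 26 lost in one arm, the open choice spans 1.60 to 0.95 at 0.5 mg, or adds 0.44 to 0.52 in the drug's favour if the losses are on placebo. At 2.0 mg the estimate moves but power hardly does. Confidence is high on the wording gap and lower on the size, because the documents give no missingness by arm or reason.

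The LOCF part is smaller. At Month 3 it concerns 6MWT and SPPB, not DXA; at Month 6 it is minor and vanishes if the effect persists. The conflict with Protocol 9.6 is plain on the text.

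A reader might infer that outcomes could be steered subject by subject. SAP 2.11 keeps individual assignments blinded after the Month 3 analysis, which limits that. Group results are known by then, however, so a rule still open could be settled with them in view.

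**What to change.** 1. In SAP 2.17, replace the sentence offering worst case or exclusion with MI of all missing Month 3 values under MAR. Put treatment, baseline, country and sex in the model, and state the number of imputations and the seed.
2. Add one pre-specified placebo-based (reference-based) sensitivity analysis that imputes subjects who stopped for treatment-related adverse events or lack of effect. Suspected MNAR values are then addressed there, so including them in the MAR step does not ignore them. Defining the worst case and a selection rule would close the wording gap but keep the weakness of a single fixed value.
3. Treat Month 3 scans that fail the stringent definition in one stated way in the MI tables.
4. In SAP 2.16, drop LOCF at Month 6. At Month 3, rely on observed data plus the planned MI for 6MWT and SPPB. Use observed data only for endpoints outside the MI list (grip strength, Borg, bone turnover markers, PADLs/IADLs).
5. Set these rules before Month 3 results by treatment group are known, and amend Protocol 9.6 to match, since the fix itself imputes.

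Cost: SAP wording, a few lines of PROC MI code, a short protocol amendment, slightly wider intervals, one extra table, and no filled-in Month 6 value for endpoints outside the MI list.
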